5.5 Study Compensation

A monetary compensation will be provided in the form of a gift card commensurate with the amount of time, inconvenience, and discomfort experienced by each participant while participating in the obtaining of the endometrial biopsies. The total possible compensation is \$125.00 (\$50 for baseline and \$75 for the 4 month assessment). Participants who are eligible based on the results of Screening Visit 2 tests will receive the first gift card of \$50.00 on the Randomization / Visit 3. Participants found to be ineligible based on baseline EMB results will be contacted by phone and gift card will be mailed to them. Second gift card of \$75.00 will be given after completion of all measurements on Post-Treatment Evaluation visit on the 4th month. For all study related assessment visits to MD Anderson each participant will receive parking validation.

5.6 Registration Process

This is a phase II, four-armed, randomized chemoprevention trial. Registration will be a two-step pre-enrollment to enrollment process.

- A. New Patient (participant) Intake form will be initiated by study research nurse during phone interview with potential participant. Once form is completed, it will be sent to the MCGOBC to schedule participant for in-person registration.

- B. At the first screening visit, participant will register in-person as a new participant at MCGOBC and will be assigned a Medical Record Number (MRN). After they have received an MRN they will meet momentarily with one of the study Gynecologist to obtain consent.
- C. Consented participants will be registered in Clinical Oncology Research (CORe) System and will be assigned a unique identifying number at entry into the trial on the first screening visit. This unique subject number will not change during the study.
- D. Only participants who meet all eligibility criteria and have successfully completed all laboratory tests and EMB will be randomized to CTC website on the third visit (see section 7.0 for details on randomization).

5.7 Participating Center

The Screening Visits (1 & 2), Randomization / Visit 3, Lifestyle intervention sessions, In-person toxicity assessments, and Post-Treatment Evaluation will occur at the University of Texas M. D. Anderson Cancer Center.

6.0 Treatment Plan

We have chosen to treat for a 4 month period. This period is based on studies demonstrating that metformin will reach full potential in the reduction of hyperinsulinemia and insulin resistance by four months.

6.1 Treatment

Prior to beginning therapy, participants will have a baseline endometrial biopsy performed. If the baseline endometrial biopsy reveals endometrial hyperplasia or cancer or if an office endometrial biopsy cannot be performed the participant will be removed from study. Women with abnormal biopsy results will be referred to contact their Gynecologist from their insurance provider for further treatment for these results.

The study is partially blinded in that investigator and participants will be blinded to the treatment of Metformin versus placebo, but will be un-blinded in regard to the lifestyle intervention. All participants will be followed for at least one month after their last dose of study medication. All treatment-related toxicities will be followed by phone until resolution. All other participants will be randomized to one of four arms:

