6.4 Toxicity assessment

The summary of toxicity assessment for in-person and phone is listed below.

A. In-person assessment include:

- physical exam (only on 1st month)
- weight
- review of study medication side effects (as listed in consent and instruct participant to call if they experience symptoms of abdominal pain, anorexia, nausea, jaundice, and change in urine color)
- ALT and creatinine levels.
- Dispense Pill Diary and prescription.

B. Phone assessment include reported symptoms of:

- gastrointestinal (abdominal pain and severe diarrhea)
- liver (jaundice) and review ALT lab results
- kidney (changes in urine color and amount) and review creatinine lab results
- heart (CHF)
- rare side effects listed in consent

The in-person toxicity assessment will be at the end of each month and will be a month from Randomization / Visit 3. All participants must agree to keep a drug administration diary (Pill Diary). This diary will be signed by both the participant and research nurse and reviewed during each clinic visit to verify compliance. The medication administration record will be filed in the participant's chart. Any discrepancies will be noted along with

the reason, if known. Any remaining pills will also be returned at each clinic visit and documented.

Participants with mild elevations in ALT (3x ULN), will continue study drug at same dose, and have another ALT drawn 30 days later. If ALT levels are \geq 4x ULN, the study drug will be stopped, and participant removed from the study. Participants with an elevation in creatinine of \geq 2.5x ULN will be taken off of the drug and removed from the study. The study drug will be stopped and participant removed from study if the participant reports symptoms of congestive heart failure (CHF) such as: fatigue, tightness or congestion in the chest, edema to ankles or lower extremities, and shortness of breath.

Telephone contacts will be made periodically as needed to assess on the first, second, third, and fourth month (plus or minus 10 days) to encourage compliance and assess for the presence of toxic or adverse effects. Participants experiencing toxic or adverse effects will be referred to MD Anderson health providers for medical care however medical care will be billed to the participant or participant's insurance provider. All participants will be contacted by telephone 4 weeks after completion of the study for follow-up and toxicity assessment.

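### Toxicities are followed to resolution by phone, but no repeat test is explicitly ordered after an ALT or creatinine stop, and Table 5 omits creatinine at months 2 and 3

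*Combined protocol and SAP*

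**What the plan says.** Section 6.1 makes two follow-up commitments. The first sets a minimum duration: "All participants will be followed for at least one month after their last dose of study medication". The second sets the method and the end point: "All treatment-related toxicities will be followed by phone until resolution".

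Section 6.4 gives the laboratory rules. At ALT of 4 times ULN or more, "the study drug will be stopped, and participant removed from the study". A woman whose creatinine reaches 2.5 times ULN or more "will be taken off of the drug and removed from the study". Neither rule requires a symptom. For a mild ALT elevation (3 times ULN) the drug continues and the woman is to "have another ALT drawn 30 days later".

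On monitoring, Section 6.4 part A lists "ALT and creatinine levels" among the contents of the in-person assessment and adds: "The in-person toxicity assessment will be at the end of each month". Section 5.4 sets those assessments at months 1, 2, 3 and 4. Part B, the phone assessment, has entries such as "liver (jaundice) and review ALT lab results", with a matching kidney entry for creatinine.

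Table 5 (Section 13.0) differs. Creatinine is marked at months 1 and 4 and blank at months 2 and 3. ALT is marked at months 1 and 4; at months 2 and 3 it carries footnote f, which limits the draw to women with an ALT elevation by CTCAE version 4.0.

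**The concern.** A toxicity that exists only as a laboratory value can be shown to have resolved only by another laboratory value. The two rules that end treatment on such a value also remove the woman from the study, and the stated method of follow-up from then on is the telephone. Followed literally, the protocol promises follow-up to resolution by a method that cannot establish it.

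The Table 5 conflict raises a related question: whether the creatinine rule can be triggered at all for much of the treatment period. Kidney function matters for this drug. Section 3.5 says about 90% of absorbed metformin leaves by the renal route within 24 hours, Section 3.8 lists renal dysfunction as a contraindication, and Section 3.7 lists lactic acidosis as a side effect.

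What is at stake is safety follow-up in the few women affected, and monitoring of all women in months 2 and 3.

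**Working it through.** The plan states no figure to reproduce. The check sets the texts side by side and counts draws.

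**Step 1: is a repeat test ordered after a laboratory-based stop?**

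- Section 6.1: phone follow-up to resolution, and at least one month of follow-up after the last dose. No sample is named.
- Section 6.4, ALT and creatinine stopping rules: stop and remove. No sample is named.
- Section 6.4 part B: results are reviewed. No sample is ordered.
- Section 6.4, end: referral to the institution's providers, billed to the woman or her insurer, and a phone call 4 weeks after completion. No sample is named.
- Section 8.0: further removal criteria, including symptoms of heart or renal failure. No sample is named.
- Section 10.3: adverse events are elicited at visits and by phone. No sample is named.
- Table 5: draws belong to scheduled visits. Nothing says these continue after removal.

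No text explicitly orders a repeat of the abnormal test after either stop.

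**Step 2: on-treatment draws under each schedule**

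| Test | Sections 6.4A and 5.4, months 1 / 2 / 3 / 4 | Table 5, months 1 / 2 / 3 / 4 |
|---|---|---|
| Creatinine | yes / yes / yes / yes = 4 | yes / blank / blank / yes = 2 |
| ALT | yes / yes / yes / yes = 4 | yes / if elevated / if elevated / yes = 2 fixed + 2 conditional |

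Difference for creatinine: 4 − 2 = 2 cells. Difference for ALT: 2 cells that are unconditional in one place and conditional in the other. In total 2 + 2 = 4 cells conflict.

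**Step 3: what the conflict does to the stopping rules**

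Under Table 5 no creatinine value exists between the month 1 and month 4 draws, so the 2.5 times ULN rule has nothing to act on in that interval. Table 2 (Section 3.4) reaches the full dose of two capsules twice daily in week 4. The month 1 draw therefore falls, nominally, about a week into full dosing, and the month 4 draw comes as the 120-day course ends. For ALT, a first rise after a normal month 1 value could go unseen until month 4 if footnote f depends on an elevation already found. Under Section 6.4A both rules can act every month.

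**The case against.** The strongest reply is that the duty exists and only its wording is loose. Section 6.1 requires follow-up to resolution. The phone assessment includes looking at ALT and creatinine results. Section 7.1 expects interim data to be available for grading. Affected women are referred to providers at the same institution, and criterion 4.1.11 requires each woman to have a primary care provider. The one-month follow-up is not limited to the telephone. A sensible investigator would retest. All of this is fair, and it keeps the point minor. But none of these texts orders a sample, so there may be no new result to review.

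A reader might infer more than the documents support:

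- *That the milder ALT elevation is followed better than the severe one.* The 30-day redraw at 3 times ULN goes with continued dosing at the same dose. It is on-drug monitoring, and nothing says it continues to resolution. It is no benchmark for follow-up after a stop.
- *That a woman stopped for ALT certainly gets no further draw.* If removal means off drug only, with visits kept, footnote f would prompt ALT at months 2 and 3 and the later scheduled draws would stand. The text does not settle this. Even then, those draws are not tied to resolution, and footnote f has no creatinine counterpart.
- *That the long interval between month 4 and the 1-year visit measures the gap.* A value first seen at month 4 arrives when dosing is ending anyway, and the interval depends on what date counts as baseline.
- *That retesting is forbidden or falls at the woman's expense.* Nothing forbids it. Billing is stated for medical care, and the consent pages are not in this copy.
- *That conditional ALT in Table 5 is a mistake.* Footnote f reads as deliberate. The conflict with Section 6.4A is real, but which text was intended is unknown.

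**Conclusion.** The point holds as a minor gap in safety follow-up. Two stop-and-remove criteria are defined by a laboratory value alone, the named route to resolution is the phone, and no repeat of the test is explicitly ordered afterwards. Separately, Table 5 and Sections 6.4A and 5.4 disagree in 4 cells. The two creatinine cells matter more, because under Table 5 the creatinine rule cannot operate between months 1 and 4; only the symptom-based removal in Section 8.3 remains in that interval.

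The conclusion about follow-up rests on reading removal from the study as not guaranteeing further study draws. The conclusion about detection applies only if staff work from Table 5. The documents give no expected rate for either stop, so no number of women can be stated. Entry criteria 4.2.2 and 4.2.3 already exclude ALT of 2 times ULN or more and creatinine of 1.4 mg/dL or more. The drug is stopped at both thresholds, and no endpoint, power figure or efficacy analysis changes.

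**What to change.** 1. In Sections 6.1 and 6.4, state that a treatment-related toxicity defined by a laboratory value is followed by repeating that test as a study procedure, at intervals of no more than 30 days, until it returns to baseline or to a level set by the investigator. State that this applies after drug stop and removal. Keep phone follow-up for toxicities defined by symptoms only, and add a matching footnote to the ALT and creatinine rows of Table 5.
2. Add creatinine at months 2 and 3 to Table 5, to match Section 6.4A.
3. Decide whether ALT at months 2 and 3 is unconditional (Section 6.4A) or conditional (footnote f), and make the two places agree.

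Cost: a few extra draws in affected women for item 1. If Table 5 is current practice, item 2 adds up to 2 creatinine draws per woman, or at most 2 × 100 = 200 in the planned 100. Item 3 adds up to 2 ALT draws per woman, again at most 200, and only if ALT is aligned to Section 6.4A. The in-person visits already take place, and Table 5 gives a 4-hour turnaround for both tests.

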6.1.1 Metformin and Lifestyle Intervention

- These participants will have a baseline endometrial biopsy.

- See Table 2 in section 3.4 for Metformin Monthly dose and duration.
- Second EMB and post study labs will be done between days 115-125 (plus or minus 10 days).
- For the lifestyle intervention, all participants will receive the intervention described below in section 6.2.

6.1.2 Metformin Placebo and Lifestyle Intervention

- These participants will have a baseline EMB at study entry.
- See Table 2 in section 3.4 for Metformin Placebo Monthly dose and duration.
- The second EMB, as well as post- study labs will be done between 115-125 days (plus or minus 10 days).
- For the lifestyle intervention, all participants will receive the intervention described below in section 6.2.

6.1.3 Metformin and No Lifestyle Intervention

- These participants will have a baseline endometrial biopsy.
- A total of four 30 day cycles (plus or minus 10 days) will be given (120 days).
- See Table 2 in section 3.4 for Metformin Monthly dose and duration.
- The second EMB, as well as post study labs will be done between 115-125 days (plus or minus 10 days).

6.1.4 Metformin Placebo and No Lifestyle Intervention

- These participants will have a baseline EMB.
- A total of four 30 day cycles (plus or minus 10 days) will be given (120 days).
- See Table 2 in section 3.4 for Metformin Placebo Monthly dose and duration.
- The second EMB, as well as post study labs will be done between 115-125 days (plus or minus 10 days).

Participants randomized to receive no lifestyle intervention (control) will be asked to continue their current eating and physical activity patterns for the duration of the study. Participants randomized to the no-lifestyle condition will be given the option of receiving all study materials and up to two meetings with the dietitian after their final assessment and up to one month after.

6.2 Lifestyle Intervention

The lifestyle intervention will use the 4 month intervention developed for the Diabetes Prevention Trial (DPT). This intervention has been found to be feasible, result in weight loss and prevention of diabetes, and produce changes in diet and physical activity. The goals of the intervention are for the participants to lose 7% of their body weight, decrease fat consumption, and increase their energy expenditure by 700

kilocalories per week (equivalent to approximately 2.5 hours per week of moderate intensity walking). Participants can choose whether they want to start with dietary or activity changes first (see Table 3 for schedule of topics), but both goal areas will be addressed.

Strategies to encourage weight loss include self-monitoring of weight and reduction of fat intake (goal: approximately 25% of calories from fat). Individuals who are not able to lose weight with these two strategies will be given a calorie goal during the seventh or eighth week of the intervention sessions in the session titled "Tip the Calorie Balance". Strategies to increase physical activity include self-monitoring, use of a pedometer to increase activity, and provision of opportunities for exercise.

The intervention is delivered as a 16 in-person sessions offered over a 4 month period, once each week. If a participant is travelling when a session is scheduled, or has some other reason why she is not able to attend, the session can be done by telephone. Participants will receive print material, worksheets, measuring utensils, a food scale, and a pedometer.

All print materials have been developed by the DPT and are available for use; they will require only minor modifications for this study. Print material and worksheets to be given to participants are provided in Appendix G. The intervention also involves providing opportunities for supervised exercise (e.g., group exercise class, group walks) at least twice a week for participants. The 16 interventions sessions will be delivered by a master's level Research Coordinator or Research Dietician who will be trained in a manner consistent with the requirements of the DPT. For quality control, 10% of the sessions he/she conducts will be audio-recorded and reviewed by [name] or a Senior Research Coordinator or Research Manager.

Table 3: Schedule of intervention sessions.

	Session
1	Welcome to the Group Lifestyle Balance Program
2	Be a Fat and Calorie Detective
3	Healthy Eating
4	Move Those Muscles
5	Tip the Calorie Balance
6	Take Charge of What's Around You
7	Problem Solving
8	Four Keys to Healthy Eating Out
9	The Slippery Slope of Lifestyle Change
10	Jump Start Your Activity Plan Make Social Cues Work for You
11	Ways to Stay Motivated

12	Preparing for Long-Term Self-Management More Volume, Fewer Calories
13	Balance Your Thoughts for Long-Term Self-Management Strengthen Your Exercise Program
14	Mindful Eating Stress and Time Management
15	Standing Up for Your Health Heart Health
16	Stretching: The Truth about Flexibility Looking Back and Looking Forward

6.3 Supervised Exercise Session

Two opportunities for supervised exercise per week will be offered for participants to increase their level of physical activity. Any other form of exercise will be arranged by the participant herself outside the institution.

6.4 Toxicity assessment

The summary of toxicity assessment for in-person and phone is listed below.

A. In-person assessment include:

- physical exam (only on 1st month)
- weight
- review of study medication side effects (as listed in consent and instruct participant to call if they experience symptoms of abdominal pain, anorexia, nausea, jaundice, and change in urine color)
- ALT and creatinine levels.
- Dispense Pill Diary and prescription.

B. Phone assessment include reported symptoms of:

- gastrointestinal (abdominal pain and severe diarrhea)
- liver (jaundice) and review ALT lab results
- kidney (changes in urine color and amount) and review creatinine lab results
- heart (CHF)
- rare side effects listed in consent

The in-person toxicity assessment will be at the end of each month and will be a month from Randomization / Visit 3. All participants must agree to keep a drug administration diary (Pill Diary). This diary will be signed by both the participant and research nurse and reviewed during each clinic visit to verify compliance. The medication administration record will be filed in the participant's chart. Any discrepancies will be noted along with

the reason, if known. Any remaining pills will also be returned at each clinic visit and documented.

Participants with mild elevations in ALT (3x ULN), will continue study drug at same dose, and have another ALT drawn 30 days later. If ALT levels are \geq 4x ULN, the study drug will be stopped, and participant removed from the study. Participants with an elevation in creatinine of \geq 2.5x ULN will be taken off of the drug and removed from the study. The study drug will be stopped and participant removed from study if the participant reports symptoms of congestive heart failure (CHF) such as: fatigue, tightness or congestion in the chest, edema to ankles or lower extremities, and shortness of breath.

Telephone contacts will be made periodically as needed to assess on the first, second, third, and fourth month (plus or minus 10 days) to encourage compliance and assess for the presence of toxic or adverse effects. Participants experiencing toxic or adverse effects will be referred to MD Anderson health providers for medical care however medical care will be billed to the participant or participant's insurance provider. All participants will be contacted by telephone 4 weeks after completion of the study for follow-up and toxicity assessment.

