3.8 Contraindications

3.9.1 Renal disease or renal dysfunction (e.g., as suggested by serum creatinine levels \geq 1.4 mg/dL [females] or abnormal creatinine clearance) which may also result from conditions such as cardiovascular collapse (shock), acute myocardial infarction, and septicemia.

3.9.2 Congestive heart failure requiring pharmacologic treatment.

3.9.3 Known hypersensitivity to Metformin hydrochloride.

3.9.4 Acute or chronic metabolic acidosis, including diabetic ketoacidosis, with or without coma. Diabetic ketoacidosis should be treated with insulin. This will be assessed based on symptoms reported and reviewed with research staff during monthly toxicity screening visits.

3.9.5 Metformin will require a two day hold if given certain contrast medicines before X-rays, CT scans, MRI, and other procedures.

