4.2.2 ALT $\geq 2.0 \times$ Upper Limit of Normal (ULN)

4.2.3 Serum creatinine $\geq 1.4 \text{ mg/dL}$

- 4.2.4 Triglycerides (fasting) ≥ 400
- 4.2.5 Known inability to participate in the ongoing appointments for the four months of the study and scheduled follow-up tests.
- 4.2.6 Significant medical or psychiatric history which would make the participant a poor protocol candidate, in the opinion of the principal investigator, for any aspect of study participation including metformin, unsupervised exercise program or dietary behavior change.
- 4.2.7 Participant reported history of congestive heart failure
- 4.2.8 Prior treatment with Metformin
- 4.2.9 Currently being treated for diabetes or meeting criteria for new diagnosis of diabetes.
- 4.2.10 Known allergy to Metformin or other biguanide (Proguanil).
- 4.2.11 Use of Aromatase Inhibitors, GNRH-agonists i.e. Lupron, Zoladex within the last 6 months
- 4.2.12 Use of SERMS (selective estrogen receptor modulators) in the past 6 months, including Tamoxifen and Raloxifen
- 4.2.13 Hormone replacement therapy within the last 6 months
- 4.2.14 Women who have been treated with chemotherapy for prior malignant disease or currently have an untreated malignancy other than non-melanoma skin cancer
- 4.2.15 Participants who have had prior radiation to the pelvis

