- a) randomized to one of the four intervention groups using the Department of Biostatistics Clinical Trial Conduct Website. See section 7.0 for details.
- b) given prescription to fill the study medication at the pharmacy at MD Anderson Cancer Center.
- c) participant will be provided education on recording and monitoring daily intake of study medication into the Pill Diary. See Appendix M for Pill Diary.

- d) review and report side effects of the study medication.

Once the participant is randomized, the research nurse will notify the pharmacist to inform them of the randomization code in order to keep study staff blinded to assignment to metformin vs. placebo.

In-person toxicity assessments will be performed at the end of the first, second, third, and fourth month (plus or minus 10 days). Phone assessments will be done periodically as needed to assess for adverse effects. At the end of the fourth month of the study, the participant will return for the **Post-Treatment Evaluation** to repeat all measurements (all blood tests, anthropometric assessments, second biopsy, and survey packet) taken at the Screening Visits (1& 2). The participant will also be given a Satisfaction Questionnaire, based on their intervention, in advance to complete and return at this visit.

One year after baseline (+/- 1 month), participants will be contacted to complete a 1 Year Follow-Up Evaluation. This evaluation will include anthropometrics assessments, including a DEXA scan, the survey packet, and blood tests collected from the 4th month visit (see Table 5: Study Parameters for the list of laboratory test to be collected for 1 year Follow-up Evaluation). During this visit, the participant will also be compensated with a parking voucher to cover the cost of parking during the visit.

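### No creatinine-based rule covers the range from 1.4 mg/dL to the stop at 2.5x ULN, and Table 5 omits the month-2 and month-3 creatinine that Section 6.4 lists

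*Combined protocol and SAP*

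**What the plan says.** **Thresholds.** Section 3.8 (item 3.9.1) names renal disease or dysfunction as a contraindication, "e.g., as suggested by serum creatinine levels" at or above "1.4 mg/dL [females] or abnormal creatinine clearance". The exclusion "4.2.3 Serum creatinine" uses the same 1.4 mg/dL. On treatment, Section 6.4 says that women with a creatinine of at least "2.5x ULN will be taken off of the drug and removed from the study". For ALT, the same paragraph adds a step below the stop: at 3x ULN women "will continue study drug at same dose, and have another ALT drawn 30 days later", and drug stops at 4x ULN.

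**Schedule.** Section 6.4 A includes "ALT and creatinine levels" in the in-person assessment. On timing, 6.4 states: "The in-person toxicity assessment will be at the end of each month". Section 5.4 agrees: "In-person toxicity assessments will be performed at the end of the first, second, third, and fourth month". Table 5 marks the in-person assessment at months 1 to 4. It marks serum creatinine at Screening Visit 1, month 1, month 4 and one year. The month-2 and month-3 creatinine cells are empty and carry no footnote.

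**The concern.** The protocol treats 1.4 mg/dL as a sign that metformin may be contraindicated, but once a woman is on drug it attaches no action to that value. If her creatinine rises above it without symptoms, whether she is held, retested or left on drug depends on the individual investigator. By the protocol's own account about 90% of absorbed metformin leaves by the kidney (3.5), and lactic acidosis is a listed side effect (3.7).

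The schedule conflict adds to this. Staff who work from Table 5 would dispense at months 2 and 3 with no current creatinine, and staff who work from 6.4 would have one. Under Table 5, a rise after month 1 would not be measured until treatment is ending.

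**Working it through.** **1. Where the stop lies.** The documents give no creatinine ULN, so a range is assumed. Stop level = 2.5 x ULN; uncovered width = stop level - 1.4.

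| Assumed ULN (mg/dL) | Stop at 2.5x (mg/dL) | Width above 1.4 (mg/dL) |
|---|---|---|
| 0.8 | 2.0 | 0.6 |
| 1.0 | 2.5 | 1.1 |
| 1.2 | 3.0 | 1.6 |

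The range closes only if 2.5 x ULN is 1.4 or less, that is at a ULN of 1.4 / 2.5 = 0.56 mg/dL or lower. The width depends on the assumed ULN. That a gap exists does not, for any ULN above 0.56.

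**2. What applies inside the range.** Section 8.3 stops drug for symptoms of renal failure, whatever the creatinine. Section 7.1 asks for a determination on continuing treatment and sets no creatinine level. Section 10.1 counts an abnormal laboratory value as an adverse event. None of these names a creatinine value, a hold or a repeat test.

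**3. The schedule, side by side (treatment months).**

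| Item | M1 | M2 | M3 | M4 |
|---|---|---|---|---|
| In-person assessment, Table 5 | X | X | X | X |
| Creatinine, 6.4 A | X | X | X | X |
| Creatinine, Table 5 | X | blank | blank | X |
| ALT, Table 5 | X | f | f | X |
| Dispensing, Table 5 | X | X | X | blank |

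The blanks do not look like a fault of text extraction. The creatinine row keeps its full number of cells, and the adjacent ALT row shows its footnote in the same two columns.

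**4. Time between on-drug creatinines.** The month-1 visit is at day 30 +/- 10, so day 20 to 40. Section 6.1 puts the post-study labs at days 115 to 125 +/- 10, so day 105 to 135.

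- Table 5: nominal 120 - 30 = 90 days; shortest 105 - 40 = 65; longest 135 - 20 = 115.
- Section 6.4: nominal 30 days; with +/- 10 days at each of two adjacent monthly visits, 30 - 20 = 10 to 30 + 20 = 50.

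**5. How informative the month-1 test is.** In Table 2, full dose (two 425 mg capsules twice daily) begins in week 4, on day 22. A day-30 sample follows 9 days at full dose (days 22 to 30), and a day-20 sample precedes it. Under Table 5 this is the only scheduled on-drug creatinine that can still change dosing, because the month-4 result arrives as treatment ends.

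**The case against.** **Other safeguards.** Beyond 8.3 and 7.1, women are told to report urine changes, phone contacts ask about kidney symptoms and review creatinine results, and item 3.9.4 has acidosis assessed from symptoms at the monthly visits. Item 3.9.1 can also be read as a standing contraindication that informs the judgement under 7.1. This stands, and it narrows the gap. It does not close it: the symptom checks miss a silent rise, Table 5 makes the phone contacts as-needed, and a review of creatinine presupposes a sample.

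**The ALT comparison.** ALT is excluded at 2x, has its first stated step at 3x and stops at 4x, so a stop level above the entry level is not an error in itself. The ALT step is also to continue and retest, so parity alone would not justify a hold. Both points are right. The case for a hold rests on 3.8, which ties 1.4 mg/dL to a contraindication.

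**The schedule.** The list in 6.4 is introduced as a summary and is not literal for every visit: it includes dispensing, which Table 5 omits at month 4. Table 5 makes ALT conditional at months 2 and 3. Table 5 could therefore be the detailed schedule that governs. Against this, 6.4 limits the physical exam to month 1 and puts no such limit on creatinine, and Table 5 gives creatinine no footnote. The documents do not settle which text prevails.

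**Size of the risk.** All women enter below 1.4 mg/dL, exposure is about 120 days, and 3.7 lists no renal side effect. This stands: the documents give no frequency of creatinine reaching 1.4 mg/dL.

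**Conclusion.** Both parts hold, as a participant-safety inconsistency of moderate weight. Between 1.4 mg/dL and 2.5x ULN (2.0 to 3.0 mg/dL for an assumed ULN of 0.8 to 1.2) there is no creatinine-based hold, repeat or stop rule. Sections 6.4 and 13.0 (Table 5) conflict on creatinine at months 2 and 3, and following Table 5 lengthens the nominal interval from 30 to 90 days.

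Three stronger readings are not supported:

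- A reader might infer that the protocol requires dosing to continue above 1.4 mg/dL, or offers no protection there. Section 6.4 is silent on that range, and 8.3 and 7.1 still apply.
- A reader might infer that women are known to be at material risk of reaching that level. No figure in the documents bears on this.
- A reader might infer that the efficacy analysis is compromised. The current text on creatinine does not change power or alpha.

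Confidence is high on the missing rule and the conflicting texts, and lower on the clinical consequence.

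**What to change.** 1. **Table 5:** mark Serum Creatinine at the 2nd and 3rd month to match 6.4, and require the result to be reviewed before drug is re-dispensed. Table 5 gives a 4-hour turnaround, so this can be done at the visit.
2. **Section 6.4:** add that at any on-study creatinine of 1.4 mg/dL or more, study drug is held and the test repeated promptly, and that drug is stopped if the value is confirmed. Keep 2.5x ULN as an immediate stop without a repeat.
3. **Consequences of the new rule:** a woman stopped at the 1.4 mg/dL level stops drug only and keeps her month-4 biopsy, labs and assessments where safe. Otherwise Section 9 would enter her as unchanged from baseline. State also that doses missed in an ordered hold do not count under 8.5. More than 4 consecutive missed doses is non-compliance there, which at 2 doses a day is any hold longer than 4 / 2 = 2 days.

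**Cost:** one short amendment to 6.4, 8.5 and Table 5. Up to 2 x 100 = 200 inexpensive blood tests at visits already scheduled, extra only relative to Table 5. One repeat test for each woman who reaches 1.4 mg/dL, and possibly a few more drug stops, whose number cannot be estimated from the documents. The rule applies to metformin and placebo alike, so blinding is unaffected.
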